9.1.1 Design Overview

This is a prospective, observational, multicenter, 30-month, Phase IV study. Sites in the US who are known to treat patients with MS will be targeted for enrollment. Patients who had decided prior to enrollment to transition from any injectable DMD to treatment with cladribine tablets under routine clinical care and who meet all eligibility criteria consistent with the approved US Prescribing Information (USPI) will receive an initial treatment course with cladribine tablets in Year 1 and are planned to receive a second course in Year 2, as per the approved USPI. Cladribine tablets are being prescribed as part of patients' standard medical care and commercial product will be used. Patients will not be provided the cladribine tablets free of charge in connection with their participation in the study. It is expected that the investigator considered the mode of action and duration of effect of the previous DMD prior to initiation of cladribine tablets. It is at the investigator's discretion to define this time period, following respective USPI. The start and end dates of each MS DMD will be recorded.

Baseline PROs, MRI and treatment adherence data will be collected before the first dose of cladribine tablets is taken. Baseline data on previous MS DMD use and relapses during the previous 2 years (or since MS diagnosis, if diagnosis <24 months) will be collected retrospectively at the Baseline Visit. All treatment decisions are at the discretion of the investigator. Patients will be followed up until the end of the observation period, irrespective if they discontinue cladribine tablets during follow-up.

During the observation period, patients will attend visits as per routine clinical practice, which are expected to happen approximately at the end of Month 2, 6 and 12 during Year 1, and at the end of Month 14, 18, and 24 during Year 2, as clinically indicated.

Post-enrollment relapse count data will be collected at Month 12 (end of Year 1) and Month 24 (end of Year 2) only. Treatment adherence data during treatment with cladribine tablets will be collected at the end of Months 1, 2, 13, and 14, while other PROs will be collected at the end of Months 6, 12 and 24.

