9.2.4 Frequency of Assessments

Table 1 lists the Schedule of Assessments. Patients are considered enrolled once the informed consent form (ICF) has been signed prior to any data collection for this study. The Baseline Visit is the visit immediately prior to the patient initiating treatment with cladribine tablets. If the sites anticipate a delay between the decision to start cladribine tablets (i.e. prescription) and patient access to cladribine tablets (i.e. due to delays in cladribine tablets availability or access), the site can perform a Screening Visit first to determine eligibility of the patient and a subsequent Baseline Visit closer to the time the patient starts taking cladribine tablets. Data entered during the Baseline Visit are considered baseline data for the purposes of analysis.

Sites are asked to enter patient follow-up data for up to 24 months after a patient received initial dose if Year 2 treatment course is not delayed and up to 30 months after initial dose if Year-2 treatment course is delayed up to 6 months. Visits will be conducted within the context of routine clinical care; thus, the timing of study visits is approximate and not mandated by the study protocol.

It is anticipated that patients enrolled in the study may not immediately start cladribine tablets after the decision to initiate cladribine tablets is made, owing to the need to first discontinue their current injectable DMD (for a time period determined by the investigator) and to potential delays in obtaining cladribine tablets in the clinical setting. The initial PRO only collection (Month 1) is intended to be obtained after the patient has started treatment with cladribine tablets. The timing of Visit 1 (Month 2) and the subsequent visits may need to be adjusted based upon the actual start date of cladribine tablets, which will be recorded by the investigator.

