^g Treatment adherence questions, based on modified versions of the MS-TAQ, will be completed by patients via ePRO: at Baseline Visit (modified for self-injectables to assess adherence during last previous injectable DMD treatment) as well as at the end of Month 1, Month 2, Month 13, and Month 14 (modified for cladribine tablets).

^h Baseline PRO scales will be completed before first cladribine tablet dose is taken.

ⁱ Adverse events, **C**, relapse count, and PDDS scores will be collected as per running page and will be recorded on an ongoing basis as new information is collected for up to 24 months (or 30 months if Year 2 treatment is delayed).

^j If Year 2 treatment is delayed, final follow-up visit may occur at Month 30.

Abbreviations: ALC=absolute lymphocyte count, BDI-FS=Beck-Depression Inventory-Fast Screen, CBC=complete blood count, DMD=disease-modifying drug, ePRO = electronic Patient-Reported Outcome, HIV=human immunodeficiency virus, JCV=John Cunningham Virus, MFIS-5=Modified Fatigue Impact Scale – 5-item version, MRI=magnetic resonance imaging, MS=multiple sclerosis, MS-TAQ=Multiple Sclerosis Treatment Adherence Questionnaire, PDDS=Patient Determined Disease Steps, PRO=Patient-Reported Outcome, SF36=36-Item Short Form Health Survey; TSQM=14-Item Treatment Satisfaction Questionnaire for Medication, USPI=US Prescribing Information, WPAI-MS=Work Productivity Activity Impairment – MS.

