- Medication log containing other MS DMD treatments (if applicable) during the study period, including medication doses and routes of administration, start dates, stop dates and reasons for discontinuation
- Relapse of MS during the study period as determined by the investigator (see Section 9.1.2.1 for a guide on definition) including date of onset, resolution of relapse and definition for relapse used
- Relapse of MS associated with hospitalization (relapse as primary diagnosis or reason for hospitalization) during the study period as determined by the investigator (see Section 9.1.2.1 for a guide on definition) including date of onset, resolution of relapse and definition for relapse used
- Relapse of MS associated with glucocorticoid use during the study period as determined by the investigator (see Section 9.1.2.1 for a guide on definition) including date of onset, resolution of relapse and definition for relapse used
- MRI scans from all MRIs performed during the study period; MRI scans are assessed by a central neuroradiology center; data includes:
- Results of neurological examination as per standard of care (Kurtzke FSS, ambulation up to 5000 meters and EDSS)
- Hematology assessment (white blood cell count, hemoglobin, hematocrit, platelet count, ALC). If the investigator assesses JCV status, these data should be recorded as well
- Pregnancy, HIV, hepatitis B, hepatitis C and tuberculosis test results
- Comorbid conditions

- AEs as a continuous log
- ePRO assessments (treatment adherence questions based on modified versions of the MS-TAQ, TSQM, SF-36, MFIS-5, BDI-FS, WPAI-MS, PDDS)

[figure not shown]
Derived and transformed data needed for the analysis are described in Section 9.7.2.

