ARR: Annualized Relapsed Rate; FAS: Full Analysis Set; GENMOD: Generalized Linear Model PP: Per Protocol; SAS: Statistical Analysis System.

\* The sensitivity analysis with the zero inflated binomial model will be considered only if the number of patients without relapses is greater than 5%.

The primary endpoint is derived from the number of relapses collected through the eCRF forms "MS Relapse Report" and "MS Relapse Report Details". A patient will have 0 relapses (at Visit 3 and /or Visit 6) if replied "No" to the leading question "Has patient experienced a new MS relapse since last scheduled or unscheduled visit? (Yes, No)". For patient replying 'Yes', the number of relapses will be derived from the records in the "MS Relapse Report Details" form. If at Visit 3 the answer to the leading question is not collected, then the number of relapses in the first year and the total number of relapses during the second year will be missing. If at Visit 6 the answer to the leading question is not collected, then the number of relapses during the second year will be missing.

For ongoing patients during the study, the Time on Study will take into account the last available date of a patient. This will be used in the interim analyses for all ARR evaluations (primary objective, sensitivity analyses and secondary analyses).

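### A patient followed for 24 months with no Visit 3 relapse answer has a missing primary ARR, even when Visit 6 is answered

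*SAP*

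**What the plan says.** **The rule.** SAP 14.1.1 derives the relapse count from a leading question answered at Visit 3 (Month 12) and Visit 6 (Month 24): "Has patient experienced a new MS relapse since last scheduled or unscheduled visit"? A *No* gives zero relapses. For a *Yes*: "For patient replying 'Yes', the number of relapses will be derived from the records in the 'MS Relapse Report Details' form". If the Visit 3 answer is absent, "then the number of relapses in the first year and the total number of relapses during the second year will be missing". The counterpart for Visit 6 is narrower: "If at Visit 6 the answer to the leading question is not collected, then the number of relapses during the second year will be missing".

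**What follows from a missing count.** SAP 14.1.4 treats the Month 24 ARR as missing when the Month 24 relapse count is missing. SAP section 9 leaves missing data unreplaced by default. SAP 14.1.4 has multiple imputation considered when more than 5% of values are missing. The missing-data column of the SAP 14.1.1 table covers only patients who discontinue early, who are analysed on their follow-up and relapses to that point. The negative binomial sensitivity analyses take the same handling.

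**Where relapses are recorded.** Protocol 9.1.1: "Post-enrollment relapse count data will be collected at Month 12 (end of Year 1) and Month 24 (end of Year 2) only". The relapse-count row of Table 1 (Protocol 9.2.4) is likewise marked only at those two visits. Footnote i of the same table says otherwise: "relapse count, and PDDS scores will be collected as per running page and will be recorded on an ongoing basis". Protocol 9.3 has each follow-up relapse recorded, "including date of onset, resolution of relapse and definition for relapse used".

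**The concern.** Among patients who remain in the study, one blank item at Month 12 removes the patient from the primary endpoint, and an answered Visit 6 does not bring the patient back. An early leaver fares better under the table's missing-data column. Any dated relapses entered on the relapse forms or a running page for such a patient would go unused, because the SAP consults the detail records only after a *Yes*.

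Two things are at stake. Precision falls with every patient lost. The ARR is also biased if an absent Visit 3 answer is related to relapsing, for example when care around a relapse moves to unscheduled visits. Imputation as specified would not restore what was observed: it imputes the whole 24-month ARR, and the minimum variable list in SAP 14.1.4 contains no on-study Year 2 relapse count.

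**Working it through.** The plan states no figure to reproduce here. The non-answer rates, the ARR of 0.2 and the frailty variance of 1 below are assumptions.

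**1. The rule as a truth table.** Take a stayer with 0 relapses in Year 1, 1 in Year 2 and 24 × 30.4375 = 730.5 days on study. With everything known, ARR = 1/730.5 × 365.25 = 0.50.

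| Visit 3 | Visit 6 | Year 1 | Year 2 (literal reading) | 24-month ARR |
|---|---|---|---|---|
| answered | answered | 0 | 1 | 0.50 |
| answered | absent | 0 | missing | missing |
| absent | answered | missing | missing | missing |
| absent | absent | missing | missing | missing |

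Once Visit 3 is absent, Visit 6 changes nothing. If *total* means the cumulative count, the third row keeps Year 2 = 1, but its last column is still missing.

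**2. Share of stayers affected.** With independent non-answer rates m3 and m6, the share with a missing 24-month ARR is 1 − (1 − m3)(1 − m6). For 5% and 5% it is 9.75%; for 10% and 5% it is 14.5%. On the literal reading these are also the shares with Year 2 missing, against 5% in both cases if Visit 6 alone decided Year 2.

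**3. Complete-case bias.** With yearly rate 0.2 and gamma frailty of variance 1:
- P(no Year 1 relapse) = 1/1.2 = 0.8333. These patients have Year 2 rate 0.2/1.2 = 0.1667 and two-year ARR (0 + 0.1667)/2 = 0.0833.
- P(Year 1 relapse) = 0.1667. These patients have mean Year 1 count 0.2/0.1667 = 1.2, Year 2 rate (0.2 − 0.8333 × 0.1667)/0.1667 = 0.3667 and ARR (1.2 + 0.3667)/2 = 0.7833.
- Check: 0.8333 × 0.0833 + 0.1667 × 0.7833 = 0.200.

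Visit 3 absent in 5% of non-relapsers and 15% of relapsers (6.7% overall): (0.7917 × 0.0833 + 0.1417 × 0.7833)/0.9333 = 0.1896, which is −5.2%.

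The reverse, 15% and 5% (13.3% overall): (0.7083 × 0.0833 + 0.1583 × 0.7833)/0.8667 = 0.2112, which is +5.6%.

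**4. What keeping Year 2 would recover.** Each affected patient now contributes a Year 2 rate. First pattern: 0.7917 × 0.0833 + 0.1417 × 0.7833 + 0.0417 × 0.1667 + 0.0250 × 0.3667 = 0.1931 (−3.5%). The reverse pattern gives 0.2069 (+3.5%). The bias shrinks but does not vanish.

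**5. Precision, with 10% absent at random.** A patient's ARR over t years has variance 0.2/t + 0.04: 0.14 for two years, 0.24 for one, 0.44 for half a year. Relative to complete data:
- Dropping the 10% multiplies the SE by 1/√0.9 = 1.054.
- Keeping one covered year gives √[(0.9 × 0.14 + 0.1 × 0.24)/0.14] = 1.035.
- Keeping only half a year gives √[(0.9 × 0.14 + 0.1 × 0.44)/0.14] = 1.102.

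The primary estimator is an unweighted mean of patient ARRs, so a very short covered period costs more precision than dropping the patient. A negative binomial model with log covered time as offset does not give such a patient full weight.

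**The case against.** **The Year 2 loss may be a matter of wording.** The Visit 3 sentence says *total*; the Visit 6 sentence does not. A cumulative count is necessarily unknown when Year 1 is unknown. This is a fair reading, and a claim that both years' counts are certainly lost goes too far. The primary ARR is missing on either reading.

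**Year 1 cannot be recovered from Visit 6.** The question looks back only to the last visit of any kind, so treating an unanswered Year 1 as relapse-free would bias the ARR downward. This stands. It justifies leaving the uncovered time missing, but not ignoring the covered time or the dated records.

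**The relapses may not be on file.** A reader of footnote i might infer that relapses are always logged and then discarded. The documents do not establish that. The footnote hangs on the adverse-events row, and it contradicts both the relapse-count row and Protocol 9.1.1. It also puts PDDS on the running page, although PDDS is an ePRO with fixed months. The SAP names two relapse forms and no running page.

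**Blank answers may be rare.** Protocol 9.2.4 says "the timing of study visits is approximate and not mandated by the study protocol", which concerns timing, not unfilled forms. Sites abstract from medical records, monitors check them, and a blank item can be queried before lock. Protocol 9.9 concedes that data may be missing but gives no rate. A missed Month 12 answer is possible; the documents do not show that it is to be expected.

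**The effect is small.** A shift of about 0.01 is modest in a single-arm study that estimates a rate. With patient SD √0.14 = 0.374, it is 0.01/(0.374/√100) = 0.27 SE at an assumed 100 patients and 0.38 SE at 200. Both bias scenarios exceed 5% missing, so imputation might be used, although the SAP does not commit to it.

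**Conclusion.** The concern holds in this form: as written, the SAP gives a stayer without a Visit 3 answer a missing 24-month ARR regardless of Visit 6, with no provision like the one for early leavers. On the stated assumptions the complete-case error is about −5% to +6% of the ARR, and the SE rises by about 5% when 10% of answers are absent at random. These figures are illustrative, because the documents give no non-answer rate and the direction depends on who lacks the answer. It should be corrected because it affects the primary endpoint and the remedy is cheap; it does not overturn the analysis.

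Two further inferences are tempting and unsupported. One is that the Month 12 and 24 restriction in Protocol 9.1.1 caused the SAP rule; nothing in either document says so. The other is that an answered Visit 6 guarantees a full observed Year 2. Read literally, its look-back may reach only to Visit 5 at Month 18, about six months.

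**What to change.** **SAP 14.1.1.**
- Derive relapses by onset date from all recorded relapse details, whether or not the Visit 3 answer is present.
- Set to missing only the interval not covered by an answered relapse question, and use the covered days as exposure. Relapses counted in the rate must have onset within those days, so that numerator and denominator match.
- Define coverage explicitly, given the look-back to the last scheduled or unscheduled visit, and apply the definition to every patient, including those with both answers.
- Do not read a blank running page as zero relapses.
- State whether *total* in the Visit 3 sentence means the Year 2 count or the cumulative 24-month count.
- Give the negative binomial model log covered time as its offset, and report it beside the unweighted mean.

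**Protocol.** Reconcile 9.1.1 and the Table 1 relapse-count row with footnote i, and name the source of the relapse count.

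**Cost.** SAP wording, one derivation rule and a protocol clarification, with no new data. The downside is added variance in the unweighted mean from patients with short covered exposure. Version 7.0 is dated 14 February 2024 and the last visit is planned for 30 March 2024, so the protocol change can do little to alter collection. The SAP rule, and queries on blank Visit 3 answers, can still be settled before the planned lock on 3 June 2024.

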## 14 Efficacy Analyses

## 14.1 Primary Endpoint: ARR

## 14.1.1 Primary Objective: Analysis of the ARR

Analysis (Analysis	Derivation	Statistical Analysis Methods	Missing data handling
Population)			
Primary endp	oint: ARR over 24 Month	S	
Primary (FAS)	ARR over 24 Months. The ARR over 24 Months of a patient is calculated as the number of relapses of the patient divided by the number of days on study for that patient and multiplied by	The population estimate will be based on the average of the ARR values for the patients in the study. The corresponding 95% CI will be reported. The Statistical Analysis Software (SAS) ® MEANS procedure will be used to compute these quantities. The following descriptive statistics will be reported: mean,	Patients discontinuing early are analyzed according to number of years of follow-up on treatment and number of relapses observed at the time of discontinuation.
Secondary (PP)	365.25. This variable will be considered to get population estimates.	SD, min, max, median, first quartile (Q1) and third quartile (Q3).	
	A relapse will be defined as per routine clinical practice as determined by the investigator		
	Time on Study (days) = (Date of Study Completion or Date of study discontinuation - Date of first dose of cladribine tablets +1)		
Sensitivity (FAS)	Model based ARR, defined as expectation of relapses divided by time on study.	The estimate of the expected ARR at Month 24 will be based on a Negative Binomial (NB) model for relapse count, with offset equal to the log of years on study and adjustment for categorical number of relapses in the last 2 years, or since MS diagnosis if diagnosis <24 months (≤1 relapse, >1 relapse). The NB regression will be computed with the SAS ® GENMOD procedure, using the dist=NB option in the MODEL statement	Same handling as for the primary analysis

Analysis (Analysis Population)	Derivation	Statistical Analysis Methods	Missing data handling
		*The estimate of the expected ARR at Month 24 will be based on a Zero Inflated NB model for relapse count, with offset equal to the log of years on study and adjustment for categorical number of relapses in the last 2 years, or since MS diagnosis if diagnosis <24 months (≤1 relapse, >1 relapse). The NB regression will be computed with the SAS ® GENMOD procedure, using the dist=ZINB option in the MODEL statement.	

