## 14.1.2Sensitivity Analyses of the ARR

For the NB model the Least Squares means estimates of the ARR at Month 24 and associated CI will be reported for patients having respectively  $\leq 1$  relapse or >1 relapse in the previous 2 years, or since MS diagnosis if diagnosis <24 months. These quantities will be obtained using the LSMEANS statement with the ILINK option.

For the Zero Inflated NB model, the following approach will be used to report the estimates of the ARR at Month 24 and associated CIs for patients having respectively  $\leq 1$  relapse or >1 relapse in the previous 2 years, or since MS diagnosis if diagnosis <24 months. The STORE statement in PROC GENMOD will be used to save the fitted model. Then the fitted model will be used in proc PLM with the SCORE statement and the ILINK and NOOFFSET option.

Standardized deviance residuals will be plotted against the linear predictor to assess the goodness of fit of the model (NB or Zero inflated NB). The STDRESDEV statement with the XBETA option in the GENMOD procedure will be used.

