## 14.1.4 Subgroup Analyses of ARR

The subgroup analyses of the primary endpoint (at Month 24 for the ARR during the follow-up period) will be conducted on the FAS population.

A subgroup analysis at Month 24 of the ARR during the follow-up period for patients completing the study and patients who drop out will be performed. Estimates and CIs for the 2 subgroups will be reported using the same method of the primary analysis.

The same analysis will be performed for patients completing the treatment and patients who do not complete the treatment (i.e., completing Year 1 treatment but not Year 2 treatment) when the number of patients in the last group is greater than 10.

A subgroup analysis at Month 24 of the ARR during the follow-up period will be performed with reference to the type of MS at screening (RRMS, aSPMS, PPMS and CIS).

For the primary outcome, the patterns of missingness will be explored. When the number of missing values is substantial (>5%), multiple imputation methodology will be considered for the analysis of the primary objective. At least 20 imputed datasets will be considered. The ARR at Month 24 for a patient will be considered missing if for that patient the number of relapses at Month 24 is missing or if the Time on Study for that patient is missing. At least the following variables will be considered in the imputation model:

- ARR at Month 24
- Type of MS at screening
- Number of relapses in the previous 2 years
- Age
- Sex
- Baseline Body Mass Index (BMI)
- Compliance

Since we have both continuous and categorical variables in the imputation model the Fully Conditional Specification method will be considered for the imputation. Predictive mean matching will be used for the imputation of the following variables: ARR at Month 24, number of relapses in the previous 2 years, age, baseline BMI and compliance. SAS code for the analysis is available in the appendices.

CCI

Cladribine CLICK-MS MS700568\_0078 Version 7.0

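### The SAP gives two incompatible rules for the primary ARR of patients who leave before Visit 3 or Visit 6: one keeps their observed relapses, the other, read literally, makes their ARR missing

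*SAP*

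**What the plan says.** **Texts that keep early leavers.** In the SAP 14.1.1 table, a patient's ARR is relapses divided by days on study, times 365.25. Days on study end at completion or at discontinuation. The population estimate is the plain average of these values in the FAS. On missing data the table says "Patients discontinuing early are analyzed according to number of years of follow-up on treatment and number of relapses observed at the time of discontinuation". The negative binomial (NB) and zero-inflated NB models take the same handling. SAP 14.1.4 adds "A subgroup analysis at Month 24 of the ARR during the follow-up period for patients completing the study and patients who drop out", with estimates and CIs by the primary method. SAP 8.2 counts loss to follow-up and withdrawn consent among the non-completers.

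**Texts that make them missing.** The notes under the 14.1.1 table derive the count from a leading question at Visits 3 and 6. "If at Visit 3 the answer to the leading question is not collected, then the number of relapses in the first year" is set to missing, and the second-year count with it. For the later visit, "If at Visit 6 the answer to the leading question is not collected, then the number of relapses during the second year will be missing". SAP 14.1.4 continues: "The ARR at Month 24 for a patient will be considered missing if for that patient the number of relapses at Month 24 is missing". Multiple imputation is considered above 5% missing; otherwise SAP section 9 leaves missing values unreplaced by default.

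**Data collection.** Protocol 9.1.1 says "Post-enrollment relapse count data will be collected at Month 12 (end of Year 1) and Month 24 (end of Year 2) only". Footnote i to Table 1 in Protocol 9.2.4 says "relapse count, and PDDS scores will be collected as per running page and will be recorded on an ongoing basis".

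**The concern.** A patient who has left before Visit 6 will normally have no Visit 6 answer. The first group of texts gives that patient an ARR; the second, applied as written, removes it. The notes are the operational text, because they name the eCRF question from which the count is built. A programmer who follows them would code leavers as missing, and the drop-out subgroup would then have no observed ARR for those patients.

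This is a single-arm study whose primary objective is to estimate one ARR, and the choice of rule changes that number. An unsettled rule can be chosen after the data are seen. The same choice decides who counts toward the 5% imputation trigger. The NB models inherit the conflict, so the sensitivity analyses do not resolve it.

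The direction of error also differs. If relapse makes leaving more likely, dropping leavers pulls a complete-case ARR down. Keeping them in an unweighted mean of patient ratios pushes it up, because a relapse followed by short follow-up yields a very large ratio. Choosing the keep rule alone therefore does not settle the matter.

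**Working it through.** **1. Rule trace.** The formula is the SAP's: ARR = relapses / days on study × 365.25, with 30.4375 days per month.

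| Patient | Keep rule | Missing rule, read literally |
|---|---|---|
| 1 relapse, leaves at Month 8 (243.5 days) | 1 / 243.5 × 365.25 = 1.5 | missing (no Visit 3 answer) |
| 1 relapse, leaves at Month 18 (548 days) | 1 / 548 × 365.25 = 0.667 | missing (no Visit 6 answer) |
| 0 relapses, leaves at either time | 0 | missing |

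One step is inferred. The SAP does not define the number of relapses at Month 24. If it means Year 1 plus Year 2, a missing Year 2 count makes it missing.

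**2. Size when relapse prompts leaving.** All inputs are assumptions: gamma-mixed Poisson relapses with dispersion 1, 24 months, exponential dropout, hazard of leaving doubled after a first relapse, 400,000 patients per cell. Complete-case is the missing rule without imputation. Mean of ratios is the keep rule with the SAP's average. Pooled is total relapses over total time.

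| True ARR | Base dropout | Complete-case | Mean of ratios | Pooled |
|---|---|---|---|---|
| 0.1 | 5% | 0.098 | 0.102 | 0.100 |
| 0.1 | 30% | 0.085 | 0.113 | 0.099 |
| 0.2 | 5% | 0.196 | 0.204 | 0.200 |
| 0.2 | 10% | 0.191 | 0.209 | 0.199 |
| 0.2 | 20% | 0.181 | 0.216 | 0.198 |
| 0.2 | 30% | 0.170 | 0.223 | 0.197 |
| 0.3 | 5% | 0.292 | 0.304 | 0.298 |
| 0.3 | 30% | 0.257 | 0.332 | 0.294 |

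Complete-case is 2% (0.098 against 0.1) to 15% (0.085 against 0.1) below truth. Mean of ratios is 1% (0.304 against 0.3) to 13% (0.113 against 0.1) above. Pooled is within 2%. Complete-case lies about 4% (0.098 / 0.102) to 25% (0.085 / 0.113) below mean of ratios. The missing rule discards 5% to 31% of observed relapses.

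With the hazard unchanged by relapse (ARR 0.2, 20% dropout), the three are 0.201, 0.200 and 0.201.

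**3. Stress case.** With a 10%, 20% or 40% chance of leaving within 15 to 60 days of each relapse (ARR 0.2), complete-case gives 0.175, 0.150 and 0.107; mean of ratios 0.237, 0.272 and 0.339; pooled 0.197, 0.193 and 0.187.

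**4. A different mechanism.** Suppose leavers simply have twice the relapse rate of completers (completer ARR 0.2, 20% leaving, uniformly over Months 1 to 24). The keep rule gives 0.239 and the missing rule 0.200. The average of patient rates is 0.8 × 0.2 + 0.2 × 0.4 = 0.24. Mean leaving time is (1/12 + 2) / 2 = 1.042 years, so the pooled rate is (0.8 × 0.2 × 2 + 0.2 × 0.4 × 1.042) / (0.8 × 2 + 0.2 × 1.042) = 0.403 / 1.808 = 0.223. Here the missing rule is again low, but the pooled rate answers a person-time question rather than a per-patient one.

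**5. Imputation.** In the ARR 0.2, 20% cell of step 2 (predictive mean matching, 20 imputations, assumed N of 100 and 200), imputing from baseline variables gave 0.180 to 0.183, against complete-case 0.179 to 0.182. Adding compliance gave 0.192 to 0.194. With leaving unrelated to relapse and N of 100, the compliance version gave 0.211 against a truth of 0.20. The compliance results depend on how compliance is assumed to behave, on which the documents give nothing.

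**The case against.** The strongest reply is that the missing rule was never meant for leavers.

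- The closing note in SAP 14.1.1 uses the last available date for ongoing patients at interim analyses. That would be pointless if an absent Visit 6 answer always voided the ARR.
- SAP section 9, on tables over time, speaks of patients still in the study who lack data.
- The missing-data column of the 14.1.1 table is the only text that names early discontinuers, and a specific rule usually governs.

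These points make the charitable reading plausible. None of them exempts leavers from the count derivation, and the undefined Month 24 count leaves the gap open.

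The reply on size has force. Protocol 9.2.3 continues follow-up after cladribine is stopped, so a relapse that ends treatment need not end observation. No passage says that relapse drives study dropout, and without such a link the estimates agree. Above 5% missing, imputation might be used and could recover part of the bias. Precision is also limited: with an SD of about 0.36 and an assumed N of 100, the 95% half-width is 1.96 × 0.36 / 10 = 0.07, twice the gap of 0.216 − 0.181 = 0.035. These points limit the claim about size. They do not remove the contradiction, and a wide interval is no reason to leave the rule for the primary estimate undecided.

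It may also be said that the mean of ratios is clearly specified and so a separate matter. It is clearly specified, but it is what the keep rule feeds, and very short follow-up makes it unstable. The NB model does not fill the gap: "For the NB model the Least Squares means estimates of the ARR at Month 24 and associated CI will be reported for patients having respectively" each prior-relapse stratum, so no overall person-time rate is planned.

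**Conclusion.** The concern holds. The SAP contains both rules with no exception for leavers and no order of precedence, and the protocol does not settle whether a leaver's relapse is on file. How often this matters depends on the dropout rate, which the supplied documents do not give.

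Under the step 2 assumptions the choice of rule moves the primary estimate by about 4% to 25%, with the truth between the two. If leaving is unrelated to relapse, the means agree and the loss is mainly discarded data. The contradiction itself is certain; the size is conditional. It should be fixed before database lock.

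**What to change.** 1. Amend the notes in SAP 14.1.1 and the missing-ARR sentence in 14.1.4. For patients who leave before Visit 3 or Visit 6, count all dated relapses from first dose to the last date with known relapse status, and end Time on Study at that same date. Define that date from recorded fields; Protocol 9.3 already collects onset dates. Reserve missing for patients with no usable post-dose relapse information for the period. Define the Month 24 count, and apply one rule to the primary analysis, the drop-out subgroup, the NB models and the 5% trigger.
2. Report total relapses over total time on study, with a CI that allows for between-patient variation, as the main estimate or at least beside the mean of patient ratios. An intercept-only NB model with a log-time offset would serve. Name the main estimate before lock, and say whether it targets a person-time or a per-patient rate.
3. Reconcile Protocol 9.1.1 with footnote i of Table 1 on when relapses are recorded.

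**Cost.** SAP wording, one derivation change and one extra estimate. No new data are needed if the running page was used. If relapses were entered only at Months 12 and 24, those before drop-out may have to be retrieved from records, or those patients stay missing. The estimate will no longer rest only on complete 24-month follow-up.
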